This proposed intervention will not directly deprescribe medications; we will not be randomizing patients to medication discontinuation. Instead, we are testing an intervention to prompt consideration of a clinical decision, analogous to a clinical reminder in the electronic health record prompting the provider to consider appropriate care. We propose an innovative approach to promote medication use review that starts by contacting the patient, not the clinician, yet the ultimate decision remains with the patient-provider dyad.

Study Aim

The study primary aim is to examine the impact of a patient-centered intervention to change provider prescribing (the primary outcome), as determined by the frequency with which medications are either deprescribed or de-escalated. Our primary outcome will be the composite of deprescribing and de-escalation of target medications, identified in pharmacy dispensing records of the Corporate Data Warehouse (CDW).

Hypothesis

The hypothesis is deprescribing will be greater for Veterans receiving the intervention brochure than for those in the historical control group.

Study sites

We will target Veterans at three primary care sites who meet eligibility criteria and are prescribed the target medication at the time of their scheduled primary care visit (in-person, video technology-based, or telephone clinics). These sites were selected based upon ability to recruit adequate samples, geographic variability, and patient population. We will include all PCPs at VA Medical Centers (VAMCs) and Community Based Outpatient Clinics (CBOCs), except for resident clinicians, as these trainees are likely to turn over during the intervention.

Randomization

Previous research, including our pilot study, revealed differences in deprescribing tendencies across providers. Thus, although our intervention intends to engage patients, our study design prioritizes comparisons of patients within the same provider to maximize power. At each intervention site, individual PCPs will be randomized to the sequence of medication cohorts. We will randomize PCPs to one of the three medication groups at the beginning of the first (month 1) and second (month 7) window and assigned them to their

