remaining medication group at the start of the third (month 13) window. Our primary comparisons are between “brochure-intervention” patients and “baseline” patients (matched in terms of eligibility) from the same provider. Each patient will only have one opportunity to receive a brochure, even if they subsequently meet eligibility criteria for receipt of a second, different brochure. This allows equal exposure to the intervention for all Veterans since the impact of a second brochure might be influenced by the first brochure.

Although our primary comparison is between patients of the same provider pre- and post-intervention, we will also collect data at non-equivalent control sites matched by geography who will not receive the intervention; all data on control patients will be from the Corporate Data Warehouse (CDW). Including additional control sites will allow us to address potential temporal trends in deprescribing over the timeframe of our study that are not due to our intervention. The use of separate control sites (rather than randomizing some PCPs at each intervention site to control conditions) was preferred due to concerns about potential contamination across intervention and control conditions within sites. For both the control sites and the pre-intervention baseline period, we will identify patients who would have been eligible for the study; patients meeting criteria for multiple cohorts will be randomly allocated to only one.

Study Cohorts

The intervention cohort will consist of eligible patients in one of the three medication groups with an upcoming PCP appointment during the study enrollment period. We will create a comparison historical control cohorts comprising eligible patients in each medication group who were seen by the same PCPs at the same sites as our intervention cohort eighteen months to one year before our intervention cohort window to allow for comparable follow-up time before the intervention commenced. Patients in the intervention cohorts will be excluded from the historical control cohorts.

Medication Groups

To be enrolled in the study intervention or control cohort, patients needed to meet eligibility criteria for one of three medication-based groups. We have selected three medication-based patient groups based upon variations in 1) type of potentially inappropriate use, 2) medication factors (potential benefit and harms of continued use), and 3) anticipated interest in deprescribing by patients and providers.

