We will query CDW for 6 months following the date of each scheduled primary care visit to assess our primary outcome of deprescribing. Based upon findings in our pilot study, medication orders may not be discontinued in electronic health records even if discussions occur in the clinic visit (e.g., the PCP tells the patient to deprescribe but does not change the order). Notably, because our primary objective is to improve safe prescribing and reduce PIMs, pharmacy dispensing data best reflects our deprescribing outcome. As per our definition, either complete cessation or dose reduction will be fulfillment of our primary outcome.

Modeling our approach after the methods of Steinman, Sussman, and Martin, we will use non-refill of the medication in the 6 months following the primary care appointment as our a priori definition of cessation, based upon dispensing dates.^{4,5} Per VA Pharmacy policy, medications are only refilled upon request, and therefore, non-refill of a medication can indicate that it was discontinued, it expired (typically one year after it was ordered), or the patient did not refill it. If the medication continues to be dispensed, we will determine any reduction in the total daily dose, indicating de-escalation (one component of our deprescribing definition). An

exception to the de-escalation rule will be for insulin, where only complete cessation will qualify since dose changes are less likely to be reflected in the order compared to oral medications.

Consistent with our conceptual framework, we will also assess patient and provider factors that may influence deprescribing. Patient factors will be obtained from CDW, and will include age, race, sex, Elixhauser comorbidities in the two years prior to the scheduled primary care visit. Provider factors include sex, discipline, age, and site.

To assess potential ADWEs, we will ascertain if the deprescribed medication is subsequently restarted or returns to original dosing. We will then query CDW for diagnoses of GI bleeding for the PPI cohort, diabetic ketoacidosis or hyperosmolar hyperglycemic state for the DM cohort, and seizure for the gabapentin cohort in the year following the index visit. Note, we consider substitution to a lower potency medication (e.g., histamine-2 receptor antagonist for a PPI) to be a neutral or desirable event and not an ADWE.

Statistical Analysis Plan (see attached statistical analysis plan for greater detail)

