Veterans receiving the intervention (brochure) and survey – Exclusion criteria have been carefully incorporated to help minimize Veteran risk prior to enrollment. Further, as noted, we are not randomizing patients to have medications withdrawn. The primary intervention is distribution of information directly to patients. It is important to note that the decision to deprescribe or not remains in the purview of the patient-provider dyad. We will provide a brief cover letter when sending the medication-specific brochure to patients, and the medication-specific brochure states multiple times to not decrease or discontinue a medication without first consulting with a clinician. We are also mailing the brochures two weeks prior to a primary care visit, so if patients decide they want to stop a medication, they will already have an appointment scheduled. Taken together with the fact that patients and providers already have the ability to make deprescribing decisions, the risk of this study is not greater than current standard practice.

Risk from breach of confidentiality – In order to assure appropriate research subject selection and high-quality data collection, all study personnel will undergo training in the study protocols. We will take all necessary steps to ensure the protection of confidential information in accordance with VA regulations and other applicable laws. All identifiable data will be protected from improper use or disclosure. Only research team members will have access to data. We will enter survey data into an electronic database with a unique identifier, removing any Protected Health Information (PHI). We will store all electronic data entirely within the VA network, which is protected by firewalls. User identification codes limit access to specific directories and files. We will not include names on audio-recordings or transcriptions, and publications will not identify individual participants or the sites from which they were recruited. We will not disclose identifiable information to any other person or entity outside VA, except as required by law, for authorized oversight of this research study, or for approved use in another study by an IRB. We will store physical data in locked cabinets within the Section of General Internal Medicine and Center for Healthcare Organization and Implementation Research (CHOIR) offices at VA Boston

Potential Benefits

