To identify dose reductions, we calculated the total daily dose (TDD) of the target medication as [dose*(quantity/days supplied)].^{1,2} Substitutions within a medication drug class (e.g., pantoprazole to omeprazole) were standardized to one medication within each class. We only compared TDD at 6 months to that at the index visit for oral medications because insulin dose adjustments are not consistently documented within the electronic health record. Combination insulin products were separated into their long acting and short acting components and analyzed separately. We allowed a 10% buffer for days' supply of PPI, sulfonylurea, and gabapentin (e.g., 33 days for a 30-day supply) to account for missed doses and 100% buffer for insulin due to dispensing requirements (e.g., minimum vials dispensed regardless of dose).

Patient factors and provider characteristics (age, gender, profession) were included as covariates in the model. Based on our conceptual model and using data from CDW, patient factors included age, race, sex, and Elixhauser comorbidities in the year prior to the scheduled primary care visit.^{4,5}

Additionally, we planned to examine whether the effectiveness of the brochure intervention was associated with target medication.

Interim & Final Analysis

Our primary comparisons were between “brochure-intervention” patients and “historical control” patients (matched in terms of eligibility) from the same primary care provider. To investigate the impact of the intervention brochure on deprescribing, Hierarchical Generalized Linear Modeling (HGLM) was used to account for the nesting of patients within providers. This approach provided information not just about the average effectiveness of the intervention, but also about how much variation there is in the intervention impact across providers. In all models, Level 1 (patient-level) intercepts and slopes were treated as random effects, and parameters were estimated with robust standard errors. Using this approach of nesting patients within providers at intervention sites, for our primary analysis, we compared the likelihood of deprescribing among patients in the pre-intervention (“historical”) period to that for patients in the intervention periods who were mailed the brochure. We predicted that intervention patients would be significantly more likely to have deprescribing than patients in the pre-intervention period with the same eligibility criteria. We then examined whether the

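### The dose-reduction baseline is taken at the index visit, two weeks after the brochure is mailed, so an oral dose reduction dispensed in between is scored as no change

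*SAP*

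**What the plan says.** **Exposure.** Protocol, Procedures to Minimize Risk: "We are also mailing the brochures two weeks prior to a primary care visit".

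**Dose reduction.** SAP, Endpoints & Covariates: "We only compared TDD at 6 months to that at the index visit for oral medications". The daily dose is computed from dispensing fields (dose, quantity, days supplied). Under Protocol, Study Measures, a dose reduction alone meets the primary outcome, except for insulin, where only complete cessation counts.

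**Cessation.** Protocol, Study Measures: "we will use non-refill of the medication in the 6 months following the primary care appointment as our a priori definition of cessation". This rests on dispensing dates and needs no baseline dose.

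**Eligibility.** Three places bear on its timing:
- Protocol, Study sites: patients "are prescribed the target medication at the time of their scheduled primary care visit".
- Protocol, Study Cohorts: the intervention cohort is "eligible patients in one of the three medication groups with an upcoming PCP appointment during the study enrollment period", and the historical controls are "eligible patients in each medication group who were seen by the same PCPs at the same sites as our intervention cohort".
- SAP, Interim & Final Analysis: the analysed intervention group is "patients in the intervention periods who were mailed the brochure".

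The SAP uses both index date and index visit without defining either. It does not say which fill supplies the index dose, and neither document describes a baseline taken before mailing.

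**The concern.** A baseline should precede exposure. Here, for one component of the primary outcome, it follows exposure by about 14 days in the brochure group. Historical patients had no brochure in the corresponding 14 days. If a brochure leads to a lower oral dose (PPI, sulfonylurea or gabapentin) that is dispensed before the visit, that lower dose is the index dose. The six-month comparison then shows no reduction, and a success of the intervention is recorded as a failure.

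Action before the visit is not far-fetched. The Protocol's Risks section foresees patients stopping a drug after reading the brochure without consulting their provider. That sentence concerns stopping rather than dose reduction, but it shows that the authors expect some response in the window.

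At stake are some attenuation of the primary contrast and some loss of power. The uncertainty about when each cohort is fixed adds a second possible bias, which could run the other way.

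**Working it through.** **1. The SAP's own power figure.** Inputs from SAP, Statistical Power: 1,990 + 894 + 758 = 3,642 brochures; 20% attrition; ICC 0.05; 20 patients per provider; baseline 4.21%; detectable rate 6.55%; two-sided alpha 0.05. No planned number of controls is given, so 1:1 is assumed.

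- Design effect: 1 + (20 − 1) × 0.05 = 1.95
- Effective n per group: 3,642 × 0.80 / 1.95 = 1,494
- Power = Φ{[(p2 − p1)√n − 1.96√(2p̄(1 − p̄))] / √(p1(1 − p1) + p2(1 − p2))}
- With p1 = 0.0421, p2 = 0.0655, n = 1,494: Φ{(0.9045 − 0.6254) / 0.3187} = Φ(0.876) = 80.9%

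This agrees with the stated 80%. The smallest detectable rate comes out at 6.52%, against 6.55% stated. Splitting 3,642 across both groups would give 7.63%, so 3,642 is the intervention group alone. The brochure excess at the detectable rate is 6.55 − 4.21 = 2.34 points.

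**2. Which pre-visit changes are lost.**

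| Change between mailing and visit | How it is scored |
|---|---|
| Patient stops and does not refill | Deprescribed (no refill after the appointment) |
| Order cancelled, patient kept in the analysis | Deprescribed (no refill after the appointment) |
| Insulin dose lowered | Not counted at any time (cessation only) |
| Oral dose cut informally, no new fill | Index dose unchanged; can still be detected at six months |
| Lower oral dose dispensed | Index dose is already the lower one; no change |

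Only the last row is a loss caused by the dose baseline.

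**3. A rough bound on that loss.** The documents give no number of pre-visit changes. The SAP says prescriptions are often filled for 90 days. Assuming 90-day fills spread evenly and few extra fills prompted by the brochure, the share of patients with a fill in the window is about 14/90 = 15.6%. Let s be the share of brochure-driven events that are dose reductions (assumed; no split is given). The largest share of the excess lost is s × 15.6%, and the observed rate is 6.55 − 2.34 × that share.

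| s | Share of excess lost, at most | Observed rate | Power |
|---|---|---|---|
| 0 | 0 | 6.55% | 81% |
| 25% | 3.9% | 6.46% | 78% |
| 50% | 7.8% | 6.37% | 75% |
| 75% | 11.7% | 6.28% | 72% |
| 100% | 15.6% | 6.19% | 68% |

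**4. At the 15% rate.** Against the 4.21% baseline the excess is 15 − 4.21 = 10.79 points. Losing 3.9% to 15.6% of it removes 0.42 to 1.68 points, for an observed rate of 14.58% to 13.32%. Power stays near 100%, even if half the excess is lost.

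**5. The opposite asymmetry.** Suppose brochure patients are fixed at mailing and controls at the visit. A brochure patient who would have stopped anyway in those 14 days counts as a success, while the corresponding control never enters the cohort. At a constant background rate over about 182 days, this is 4.21 × 14/182 = 0.32 points in favour of the brochure, or 0.32/2.34 = 14% of the excess.

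**The case against.** The strongest reply is that the loss needs an unlikely sequence: a lower dose must be both prescribed and dispensed within 14 days, ahead of a visit already booked. Refills are made only on request, and the brochure repeatedly tells patients to change nothing before consulting. This stands as an argument that the effect is small. It does not remove the post-exposure baseline, and the documents contain no sensitivity analysis that would show its size.

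The power figures are also unfavourable by construction. They treat the smallest detectable rate as the true rate, and the loss shares are assumed. Both remarks are fair. A loss above 15.6% of the excess would need extra fills prompted by the brochure, for which the documents give no basis.

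A reader might infer that all responses before the visit are lost. The documents do not support that: cessation is read from refills after the appointment, whatever the state of the order, and insulin is not subject to the dose comparison.

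A reader might also infer from the Study sites sentence that mailed patients whose prescription ends before the visit are dropped. That sentence stands alone. Mailing requires selection beforehand, the SAP analyses those mailed, and neither document describes re-screening at the visit. It is a conflict of wording to resolve, not proof of exclusion.

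**Conclusion.** The point holds for dispensed oral dose reductions. The index-visit baseline is post-exposure in the brochure group and has no counterpart in the historical controls, so the dose-reduction component is biased towards no effect. Background dose changes in the same 14 days are missed in both groups and are not part of the problem.

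The bias is probably small. Under the assumptions of 90-day fills, few brochure-prompted fills and 1:1 allocation, at most 3.9% to 15.6% of the effect is lost. That matters near the 6.55% detectable rate and hardly affects power at 15%, where the estimate is still somewhat too low.

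It would be tempting to conclude that the primary contrast as a whole is biased towards no effect. That is not shown. If the cohorts are fixed at different times, background stopping favours the brochure by about 0.32 points (constant rate assumed), which is of the same order as the dose loss of up to 0.1556 × 2.34 = 0.36 points. The net direction is uncertain until eligibility timing is stated.

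**What to change.** Use one index rule for both cohorts: the mailing date for brochure patients, and the scheduled visit minus 14 days for historical controls. Then:

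- Take eligibility and baseline daily dose from the last dispensing before that date.
- Keep everyone mailed, and define controls by scheduled rather than completed visit. The SAP's 20% allowance for brochure recipients who do not attend would otherwise have no match among controls who were seen.
- Leave the end of follow-up at six months after the scheduled visit.
- Define the index date once, and reconcile the Study sites sentence in the Protocol with its Study Cohorts section and the SAP's description of the analysed group.
- Report the visit-based baseline as a sensitivity analysis. Add a count of patients whose dispensed dose fell between mailing and visit, and the corresponding count in controls; this replaces the assumed bound with an observed figure.

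The cost is a second data pull from existing CDW records and slightly more analysis work. No new data are needed.

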intervention effectiveness was moderated by the target medication. We did not expect a discontinuation rate of 100%, as patients may have an indication to remain on the medication. No adjustments were made to p-values or confidence intervals for multiple comparisons for the primary outcome.

No interim analyses were planned.

Missing Data

We examined the incidence of missing data by medication cohort (PPI vs. DM vs. Gaba). We expected very low rates of missing data, given that our primary analyses rely on CDW data. For missing data, we implemented a series of sensitivity analyses using imputation (coding as “missing” for categorical variables and imputed means for continuous variables) to assess the degree of bias that might be induced by missing data. The results did not change in direction or significance.

Methods for dealing with data transformations

We did not apply any data transformations. All data underwent standard preliminary visualization and quality screening to test for potential violations of assumptions (e.g., distributional assumptions regarding normality, homogeneity of variance, linear relationships, outliers, ceiling/floor effects).

Other analytical subsets

The intervention is designed to target and engage patients, but it is possible that the intervention may be more effective with certain providers. Therefore, a null hierarchical model was used to estimate intraclass correlations to characterize the percent variance explained at the patient, provider, and site levels.

We used HGLM to examine whether the likelihood of deprescribing changes over time at our control sites (instead of from the pre-intervention period) to rule out alternative explanations for the effect of our intervention that rely on temporal trends in deprescribing unrelated to our intervention (e.g., other deprescribing initiatives). We elected not to include temporal deprescribing trends in the manuscript since there was no evidence of significant temporal trends.

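### The covariates the SAP lists for the pooled primary model omit medication group, so the before-after estimate is open to a change in drug mix between periods (minor; size and direction unknown)

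*SAP*

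**What the plan says.** SAP, Endpoints & Covariates: "Patient factors and provider characteristics (age, gender, profession) were included as covariates in the model". The same section spells out the patient side: "patient factors included age, race, sex, and Elixhauser comorbidities in the year prior to the scheduled primary care visit". Neither list contains medication group.

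SAP, Interim & Final Analysis: the primary analysis compares historical with brochure patients within provider, across all three drug groups. Only afterwards does it examine whether "intervention effectiveness was moderated by the target medication". The protocol's Statistical Analysis Plan section has the same order.

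Protocol, Study Cohorts: historical cohorts are built for each medication group from the same providers and sites. One rule then applies to the historical side only: "Patients in the intervention cohorts will be excluded from the historical control cohorts".

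The documents also give reasons to expect the drugs to differ:
- Protocol, Medication Groups: the groups were chosen partly for variation in "anticipated interest in deprescribing by patients and providers".
- Protocol, Study Measures: insulin is an exception to the dose-reduction rule, "where only complete cessation will qualify since dose changes are less likely to be reflected in the order compared to oral medications".
- SAP, Endpoints & Covariates: there is a "100% buffer for insulin due to dispensing requirements", against 10% for the oral drugs.

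**The concern.** A pooled before-after difference mixes two things: change within each drug, and change in the share each drug contributes. Only the first can be a brochure effect. A medication term in the model separates them; the listed covariates do not.

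The documents contain one plausible route to a change in mix. Removing brochure patients from the historical cohorts thins each drug's history by the proportion of its patients who are seen and qualify again. If that proportion differs by drug, the historical mix moves away from the brochure mix.

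Provider random effects do not prevent this, because the mix can shift within a provider. The moderation analysis gives within-drug effects free of mix, but it does not correct the pooled estimate, which is the primary result.

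**Working it through.** **Inputs from the documents (SAP, Statistical Power).** Projected brochure counts are 1,990 PPI, 894 diabetes and 758 gabapentin, total 3,642. Shares: 1990/3642 = 54.6%, 894/3642 = 24.5%, 758/3642 = 20.8%. Overall baseline rate 4.21%; detectable rate 6.55%; difference 2.34 points. ICC 0.05, 20 patients per provider, 20% attrition.

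**The plan's own figure.** The SAP gives no ratio of historical to brochure patients; I assume 1:1 here.
- Design effect = 1 + 19 × 0.05 = 1.95. Effective n per period = 3642 × 0.80 / 1.95 = 1,494.
- Mean rate 5.38%. SE under the null = √(2 × 0.0538 × 0.9462 / 1494) = 0.825 points. SE under the alternative = √((0.0421 × 0.9579 + 0.0655 × 0.9345) / 1494) = 0.824 points.
- z = (2.34 − 1.96 × 0.825) / 0.824 = 0.88, so power is 81%, against 80% stated. The figure reproduces and is not in dispute.

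**Mix component: assumptions.** None of these is in the documents.
- Before exclusion, the historical mix equals the projected brochure mix.
- Exclusion removes 30% of patients on one side (PPI, or the other two drugs) and 40% or 50% on the other.
- Removal leaves each drug's own rate unchanged. This isolates the mix component and is revisited under the objection.
- Drug rates average 4.21% at the projected mix, in four patterns relative to PPI: both other drugs 1.5 times; both 2 times; diabetes 0.67 and gabapentin 1.5 times; diabetes 0.5 and gabapentin 2 times.

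**Formulas.**
- If both other drugs are k times PPI, PPI rate = 4.21 / (0.5464 + 0.4536k). For k = 1.5 the rates are 3.43% and 5.15%; for k = 2, 2.90% and 5.79%.
- In the other two patterns the PPI/diabetes/gabapentin rates are 4.12/2.75/6.18% and 3.88/1.94/7.76%. The two non-PPI drugs together then average about 4.32% and 4.61%.
- PPI share after exclusion = 0.5464(1 − e₁) / [0.5464(1 − e₁) + 0.4536(1 − e₂)], where e₁ and e₂ are the fractions removed from PPI and from the others. Example, 50% v 30%: 0.2732 / (0.2732 + 0.3175) = 46.2%.
- Shift in historical rate = (54.64% − new PPI share) × (non-PPI rate − PPI rate). Example, k = 2: 8.39 points of share × 2.90 points of rate / 100 = 0.243 points.

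**Results: shift in the historical rate, percentage points.**

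| Removed, PPI v others | PPI share after | both 1.5× | both 2× | DM 0.67×, Gaba 1.5× | DM 0.5×, Gaba 2× |
|---|---|---|---|---|---|
| 40% v 30% | 50.8% | +0.066 | +0.111 | +0.008 | +0.028 |
| 50% v 30% | 46.2% | +0.144 | +0.243 | +0.017 | +0.061 |
| 30% v 40% | 58.4% | −0.065 | −0.110 | −0.008 | −0.028 |
| 30% v 50% | 62.8% | −0.140 | −0.236 | −0.016 | −0.059 |

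A positive shift raises the historical rate, so the mix component understates the brochure effect; a negative shift overstates it. The range is about 0.01 to 0.24 points either way. The largest value is 0.243 / 2.34 = 10.4% of the planned difference. With equal removal shares or equal drug rates, every entry is zero.

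**The case against.** Four objections carry weight.

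**The design already ties the mixes together.** Both periods are matched on eligibility within the same provider, eligibility is defined by drug group, and every provider rotates through all three drugs. This stands as a reason to expect no large shift. It makes patients comparable within a drug but does not fix the drug shares. Nor is random allocation of historical patients eligible for several groups a material route to a shift; the randomised drug order roughly matches it.

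**Age and comorbidities partly stand in for drug.** The diabetes group is defined by diagnosis and, commonly, by age 65 or over. This also stands, but only as a partial proxy; it does not separate PPI from gabapentin.

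**The insulin rules point to a lower diabetes rate.** Both make deprescribing harder to record, so setting diabetes above PPI is not the natural reading. This stands. With diabetes below PPI and gabapentin above it, the shift is only about 0.01 to 0.06 points.

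**The exclusion rule may also select on outcome.** Patients who qualify again a year or more later are more likely not to have been deprescribed. Suppose their rates were 10% below their drug's average (assumption). Each kept rate is then p(1 − 0.9e)/(1 − e). For 30% v 40% removed and k = 1.5: PPI 3.43 × 0.73/0.70 = 3.58%, others 5.15 × 0.64/0.60 = 5.49%, weighted 0.584 × 3.58 + 0.416 × 5.49 = 4.37%. Over the four scenarios with more non-PPI patients removed (k = 1.5 or 2) the historical rate is 4.27% to 4.37%, above 4.21%, so the overstatement in the lower half of the table disappears. This stands, and it means the table is one component and not the net effect of the rule.

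A reader might infer that the omission inflates the brochure effect or the false-positive rate, or costs a stated amount of power. The documents support none of these. Direction is unknown. A power figure would rest on the assumed 1:1 ratio and on 1,494 effective patients per period, while the scenarios remove 35-41% of historical patients.

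**Conclusion.** The point holds as a minor one. As listed, the primary-model covariates do not protect the pooled estimate against a change in drug mix, and nothing else in the plan fully does so. Whether any bias exists, which way it runs and how large it is cannot be established from the documents.

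The figure of 0.01 to 0.24 points, at most about a tenth of the planned difference, rests wholly on assumed removal shares and rate ratios. It describes the mix component alone, and no power or false-positive figure should be attached to it. Larger assumed shifts would give larger numbers, but the documents offer no basis for them.

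A reader might also infer that no drug term was fitted. The SAP does not establish that; it shows only that none is listed.

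**What to change.** Add medication group as a fixed effect in the pooled model, and tabulate drug mix by period (historical v brochure). The SAP's Missing Data section already reports outcomes of analyses ("The results did not change in direction or significance"), so present the adjusted model as a post hoc sensitivity analysis beside the original primary estimate. If the fitted model already held a drug term, one sentence saying so is enough. If the table shows a stable mix, it largely closes the question.

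Report a risk difference averaged over the drug mix alongside the odds ratio, because adding a covariate slightly changes what the odds ratio means.

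The cost is one model run with two more parameters, one table and the post hoc label. The variable is already held, since the moderation and missing-data analyses both use it. The change does not remove selection on outcome within a drug that the one-sided exclusion may cause; that limitation should be stated separately.
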